## 4 STUDY OBJECTIVES

### 4.1 Objectives

Evaluate the preliminary safety and performance of the ANET Electrosurgery Applicator (ANET) during and after bronchoscopic ablation of a target pulmonary nodule/tumor.

#### 4.1.1 Primary Endpoints

Safety provided by the evaluation of peri-procedural device related adverse events produced by the ANET device used to ablate a target pulmonary nodule/tumor.

#### 4.1.2 Secondary Endpoints

- 1) Pathological and immuno-histochemical evaluation of the acute thermal effect, produced by the ANET device, on targeted pulmonary nodule/tumor and surrounding tissue to determine if the observed zone of ablation is localized and consistent with the predicted zone of ablation.
- 2) Characterize any effects on surrounding tissue outside the zone of predicted ablation.

#### 4.1.3 Observational Endpoint

Characterization of possible immune response changes.

## 5 STUDY PLAN

### 5.1 Study Design

This is a first in human use pilot study. Study subjects who are already scheduled for a surgical resection (lobectomy or greater) of their target nodule/tumor, as standard of care, will be treated with the ANET device. The target ablation zone will be entirely within the planned resection. Following ANET ablation, the subject will undergo their scheduled lung resection. The ablated target nodule/tumor will undergo gross, immuno-histochemical and histopathologic assessment.

### 5.2 General Description of Study

[figure not shown]
After consent and evaluation of all inclusion and exclusion criteria, subjects will be enrolled in the study. The subject will undergo standard pre-operative testing, per the study institutional requirements. At that time, subject vital signs will be recorded. The subject will be prepped for bronchoscopy.

A pre-ablation chest CT will be taken. The target nodule/tumor will be accessed via EBUS bronchoscopy, which may be guided and confirmed with Cone Beam CT, Intra-operative CT, or fluoroscopy, and ablated using the ANET Electrosurgical Applicator. Following ablation, there will be a bronchoscopic exam of the treated region and repeat chest CT will be taken.

Immediately following bronchoscopy and ablation of the target tissue, the subject will undergo the planned surgical resection. The ablated tumor will be prepared for histopathological and immuno-histochemistry evaluation to assess the area of ablated tissue. Subjects will be followed peri-operatively. There is no long-term follow-up since the ablated tissue will be resected during the surgical procedure, however adverse events will be captured through 30 days post procedure.

Blood will be drawn pre and post-ablation and 2-4 weeks post-surgery, per the ANET Blood Draw Lab Manual, DN0042775, to evaluate for potential immune response indicators. Blood specimens will be analyzed by a core laboratory to characterize cells important in immune responses and the disease process.

A study diagram is shown in Figure 4 below.

### 5.3 Study Duration

The study duration is anticipated to be approximately 2 years.

## 6 SUBJECT POPULATION

Adult subjects with confirmed Stage I or Stage II primary lung cancer with a pulmonary nodule/tumor suitable for ablation, by the ANET device via EBUS bronchoscopy, prior to planned surgical resection.

### 6.1 Eligibility Criteria

The criteria listed below shall be used to determine if an individual is eligible for enrollment in this clinical study.

#### 6.1.1 Inclusion Criteria

1. Subject with Stage I or Stage II primary lung cancer
2. Pathological proof of target nodule/tumor type and malignancy with specimen considered adequate for mutational analysis per institutional laboratory standards
3. Target nodule/tumor which can be accessed via EBUS bronchoscopy
4. Resection/surgical candidate (lobectomy or greater) as standard of care
5. Participants must be at least 22 years old and able to provide consent

#### 6.1.2 Exclusion Criteria

1. Subjects in whom flexible bronchoscopy is contraindicated
2. Target nodule < 1.0 cm
3. Prior radiation or neo adjuvant chemotherapy of the target nodule/tumor
4. Any comorbidity that the investigator feels would interfere with the safety of the subject or the evaluation of study objectives
5. Pacemaker, implantable cardioverter, or other electronic implantable device
6. Patients with coagulopathy
7. Patients in other therapeutic lung cancer studies
8. Subject is pregnant or breastfeeding
9. Known or suspected sensitivity or allergy to nickel

## 6.2 Assignment of Subject Identification

Each subject who has signed an informed consent will be assigned a subject ID number unique to the subject and study site.

## 7 STUDY PROCEDURES AND PATHOLOGY METHODS

### 7.1 Informed Consent

Subjects must sign the informed consent prior to enrollment. The original consent form will become an integral part of each case report form file. One copy will be retained with the subject's medical records and one copy will be provided to the subject.

### 7.2 Procedure

All study eligible subjects will be prepared for the bronchoscopic/surgical procedure according to the policies and procedures established by the institution.

Before starting the procedure, a "time out" review will take place. During the "time out" session, the nodule/tumor to be treated will be noted by all in attendance.

#### 7.2.1 Pre-ablation CT and blood draw

A pre-ablation chest CT will be taken prior to ANET ablation, may be performed while the subject is under general anesthesia.

A pre-ablation blood draw will be taken to assess for immune response indicators

#### 7.2.2 ANET Procedure

The ANET Applicator and RF generator will be prepared for use per the ANET Instructions for Use (IFU). ASA guidelines for the Prevention and Management of Operating Room fires will be followed, including:

- Discuss the use of RF prior to the procedure with the anesthesiologist and collaborate with procedure team throughout the procedure
- Use cuffed tracheal tube
- Before RF ablation:
  - Announce the intent to start RF ablation
  - Reduce the oxygen concentration to the minimum required to avoid hypoxia, guided by patient monitoring
  - Stop the use of nitrous oxide
- Wait a few minutes before authorizing the use of RF ablation
- Refer to institutional requirements

The nodule/tumor will be accessed via EBUS bronchoscopy. If the nodule/tumor cannot be accessed via EBUS, or nodule/tumor is considered inappropriate for ablation by the treating physician, the subject will proceed to surgery and will not count against enrollment.

Under visualization with the EBUS bronchoscope, the ablation zone path length of the nodule/tumor will be measured using the EBUS measurement tool. If the path length is less than 1 cm, then a new ablation zone in the target nodule/tumor will be identified. The center of the ablation zone, should be at least 2 cm away from any critical structures, as determined by the investigator.

If an acceptable ablation zone cannot be determined, the subject will be considered a treatment failure. Tissue ablation parameters will be determined by the IFU.

The ANET applicator will be advanced to the target nodule/tumor under EBUS visualization. After the needle has been advanced into the target location, position may be confirmed using cone beam CT, intra-operative CT or fluoroscopy. The needle should be deep enough in the tissue and not extend past the distal margin of the target nodule/tumor. If it is not possible to place the needle appropriately, the subject will be considered a treatment failure.

Once the needle is placed correctly, a fixed electrode spacing of 1mm should be maintained for ablation. The target nodule/tumor can then be ablated per the energy application guidelines in the IFU. Saline flow post-RF delivery must be maintained to bring the tissue next to the electrode to baseline temperatures ( $\sim \geq 120$  s) and to arrest thermal damage to stated margins.

If the tumor is greater than 3.1 cm, than the energy parameters for no greater than a 3.1 cm ablation zone will be used.

### 7.2.3 Post-ablation bronchoscopic evaluation and CT

A post-ablation bronchoscopic evaluation and chest CT will be taken following ANET ablation, while the subject is under general anesthesia.

### 7.2.4 Post-ablation blood draw

A post-ablation blood draw will be taken to assess for immune response indicators. The blood draw should occur prior to the surgical resection.

### 7.2.5 Surgical Resection

Surgical resection will be performed as scheduled, per institutional guidelines.

Following resection, the ANET ablated tumor will be grossly evaluated and prepared for histopathologic and immuno-histochemistry evaluation of the treated tumor.

### 7.2.6 Pathology

The tumors will be bisected through the largest diameter in a right angle referring to the RFA electrode direction and marked to determine orientation of coagulation electrode immediately after the resection procedure. The specimens will be fixed in 10% neutral buffered formalin-solution and prepared for routine diagnostics and immuno-histochemistry.

The specimens will be examined by gross pathology, histopathology, and may be examined by immuno-histochemical methods. Routine staining will be performed with hematoxylin and eosin (H&E). Analysis of cellular vitality may be performed with different methods of staining, which may include one or more of the following: mouse antihuman mitochondria monoclonal antibody (MAB 1273; Millipore UK, Hertfordshire, UK), Terminal deoxynucleotidyl transferase-mediated nick end-labeling (TUNEL; Boehringer Ingelheim, Germany), antibody MiB1(Ki67; Dianova, Hamburg Germany), PHH3, and Masson's trichrome The immuno-histochemical criterion for cell death in is the lack of expression or proliferation/mitotic index markers in the treated and surrounding tissue. The intent of the pathology assessments is to determine if the observed zone of ablation is consistent with the predicted zone of ablation and to characterize any effects on surrounding tissue outside the zone of predicted ablation.

---

 Schneider et al., "Intraoperative Radiofrequency Ablation of Lung Metastases and Histologic Evaluation."

 Thomas Schneider et al., "The Efficacy of Bipolar and Multipolar Radiofrequency Ablation of Lung Neoplasms - Results of an Ablate and Resect Study," *European Journal of Cardio-Thoracic Surgery: Official Journal of the European Association for Cardio-Thoracic Surgery* 39, no. 6 (June 2011): 968–73, doi:10.1016/j.ejcts.2010.08.055.

 Clasen et al., "Pathomorphologic Evaluation of Pulmonary Radiofrequency Ablation."

 Ibid.

 Pelosi et al. *J Thorac Oncol.* 2014;9: 273–284

 Ozturk Sari et al. *Endocr Pathol.* 2016 Jun;27(2):162-70

 Jie Ouyang et al. Utility of desmin and a Masson's trichrome method to detect early acute myocardial infarction in autopsy tissues, *Int J Clin Exp Pathol* 2010;3(1):98-105.

 T.D. Koreckij et al., Low Dose, Alternating Electric Current Inhibits Growth of Prostatic Cancer, *The Prostate*, Accepted 5 October 2009, Published online in Wiley InterScience (www.interscience.wiley.com).

The micro environment of the resected tissue may have pathological assessment for immune cell population to explore a potential mechanistic effect of immune response..

The pathologic and immuno-histochemical effect of RFA on nodules/tumors and surrounding tissue will be evaluated by an experienced pathologist.

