## 2 DEVICE DESCRIPTION

### 2.1 Device Overview

[figure not shown]
The Active Needle Endoscopic Treatment (ANET) Applicator is a disposable bipolar electrosurgical applicator used for the coagulation and necrosis of soft tissue. Each Applicator consists of a 19 gauge needle (proximal electrode) with a coil (distal electrode). The needle and coil serve as the bipolar electrodes, so there is no need for an external ground pad.

The ANET Applicator works with ancillary equipment which include an ultrasound endoscope and a compatible electrosurgical generator. The ANET Applicator has been shown to be compatible with the previously cleared/approved Olympus ESG-100 or Olympus ESG – 300 Electrosurgical Generator. Other radiofrequency generators will be added as compatibility is established.

A standard infusion pump can be used to infuse small quantities of saline during active ablation. Saline is administered to cool the electrodes during ablation, and to prevent the tissue surrounding the target tissue from dehydration.

To perform ablation, the flexible portion of ANET device is first inserted into an ultrasound endoscope with a working channel of 2.2mm or greater, then locked onto the adapter biopsy valve on the endoscope using the endoscope adapter on the handle. The handle facilitates advancement of the sheath and needle/proximal electrode during puncture of the target tissue. Once the needle is positioned in place, the handle is used to facilitate advancement and of the coil. The coil in the target tissue and helps to hold the device in place during treatment.

To perform ablation, the bipolar plug on the ANET Applicator is connected to the compatible electrosurgical generator. The generator is set to the appropriate power level included in the Instructions for Use (IFU). During ablation, radiofrequency (RF) current is passed between the distal electrode and the proximal electrode to thermally coagulate the tissue. Once the target energy has been reached, ablation is stopped, and the electrodes are retracted from the target. Additional ablations can be performed to achieve a larger coagulation zone.

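### The only cut that 7.2.6 specifies is placed by the tumour, not by the ablation zone, so the specified face can understate or miss a zone and shows nothing of its extent along the needle

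*Combined protocol and SAP*

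**What the plan says.** **The cut.** Section 7.2.6 (Pathology): "The tumors will be bisected through the largest diameter in a right angle referring to the RFA electrode direction". The same sentence has the tumour "marked to determine orientation of coagulation electrode immediately after the resection procedure". It gives no slice interval, no further plane and no rule for measuring the zone.

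**Its purpose.** The same section says the pathology is "to determine if the observed zone of ablation is consistent with the predicted zone of ablation" and is also to describe effects outside the predicted zone. These are secondary endpoints 1 and 2 in section 4.1.2.

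**Where zones are placed.** Section 7.2.2 measures the path length by EBUS: "If the path length is less than 1 cm, then a new ablation zone in the target nodule/tumor will be identified". The zone centre "should be at least 2 cm away from any critical structures". For large tumours, "If the tumor is greater than 3.1 cm, than the energy parameters for no greater than a 3.1 cm ablation zone will be used". The synopsis (Treatment Algorithm) limits the first 3 subjects to one zone; after that the number of zones depends on tumour size and the physician's target.

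**The electrode.** Section 2.1: "Once the target energy has been reached, ablation is stopped, and the electrodes are retracted from the target". Resection follows.

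**The concern.** The plane is located by a feature of the tumour, while the quantity of interest is the zone. The zone is positioned by path length, clearance and physician choice; it may fill only part of a large tumour, and there may be more than one. No rule brings its centre onto the tumour's largest diameter.

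The plane also runs at right angles to the electrode. Even a perfectly centred face shows width only, not length along the needle. That direction matters: the long-term animal study in section 3 reports occasional thermal injury to the bronchial mucosa from heated saline tracking back along the needle, confined to the immediate penetration site.

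Finally, the angle of the cut depends on an electrode that has already been removed. The specimen is to be marked for orientation after resection, but no section says how the direction reaches the person who cuts.

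At stake is the observed half of the observed-versus-predicted comparison. With about 10 subjects and summary reporting only (section 12), a few misread zones would visibly change the result, and a specimen cannot be cut again from scratch.

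**Working it through.** The documents give no sectioning figure or size tolerance, so there is no plan figure to reproduce. The check is plane geometry.

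**Inputs from the documents:** minimum path length 1 cm and zone cap 3.1 cm (7.2.2); no upper tumour size in the eligibility criteria (6.1).

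**Assumptions:** spherical zone of diameter D; roughly spherical tumour of diameter T cut through its centre; the 2.0 cm zone, the offsets and the values of T are illustrative.

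**1. Off-centre cut.** At distance h from the zone centre, observed diameter = √(D² − 4h²).

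| D (cm) | h (cm) | Calculation | Reads (cm) | Error |
|---|---|---|---|---|
| 2.0 | 0.5 | √(4 − 1) | 1.73 | −13% |
| 3.1 | 0.5 | √(9.61 − 1) | 2.93 | −5% |
| 3.1 | 1.0 | √(9.61 − 4) | 2.37 | −24% |

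The zone is missed when h ≥ D/2.

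**2. Tumour size these offsets need.** If the zone lies wholly inside the tumour, the largest possible offset is (T − D)/2, so T must be at least D + 2h.

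- 2.0 cm zone, 0.5 cm off: T ≥ 2.0 + 1.0 = 3.0 cm.
- 3.1 cm zone, 1.0 cm off: T ≥ 3.1 + 2.0 = 5.1 cm.
- Complete miss: (T − D)/2 ≥ D/2, so T ≥ 2D.
- 3.1 cm zone in a 4 cm tumour: largest h = 0.45 cm; √(9.61 − 0.81) = 2.97 cm, a loss of about 4%.
- 3.1 cm zone in a 5 cm tumour: largest h = 0.95 cm; √(9.61 − 3.61) = 2.45 cm (79% of true).

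These are worst cases for each tumour size. If the zone centre is equally likely to be anywhere that keeps the zone inside the tumour (a further assumption, checked by simulation), the 3.1 cm zone in a 5 cm tumour reads on average about 96% of its true diameter.

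**3. Tilted cut.** For a zone of length L along the needle and width W, a central cut tilted by angle t reads a width of 1/√((cos t/W)² + (sin t/L)²). With an assumed L = 3.1 and W = 2.0 cm:

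- 30°: 1/√(0.1875 + 0.0260) = 2.16 cm (+8%).
- 45°: 1/√(0.1250 + 0.0520) = 2.38 cm (+19%).

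The error can therefore go either way.

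**4. Extent along the needle.** A plane at right angles to the needle contains no length along it. If the EBUS path length runs along the needle, the dimension used for planning is the one this face cannot show.

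**The case against.** Several stronger conclusions are tempting, and the documents do not support them.

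- **A reader might infer that only one cut will be made.** The text also mentions preparation for routine diagnostics, gross pathology and histopathology. None of this bars further sections. What stands is that none is required and the measuring face is not named.
- **A reader might infer that the two conditions on the plane contradict each other,** since a plane at right angles to the electrode contains the tumour's overall largest diameter only if that diameter is itself at right angles to it. The sentence reads naturally as choosing, among planes at right angles to the electrode, the one where the tumour is widest. That is always possible.
- **A reader might infer that the needle direction cannot be recovered from the specimen.** The documents do not say so. The plan calls for an orientation mark, a 19-gauge puncture may be visible, and a bronchoscopic examination and CT follow ablation (7.2.3). But a mark that preserves direction does not fix where along the track the cut falls, and no hand-over of the information is described.
- **A reader might infer a consistent bias towards a finding of a localised effect.** Understatement holds for an off-centre parallel cut of an idealised shape, whereas section 3 describes variable patterns. Understatement also counts against agreement with the predicted zone, and tilt works the other way.

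Two further points limit the size. Energy is set by nodule size, which tends to keep zone and tumour comparable. Repeat ablations are described in section 2.1 as a way to enlarge the coagulated area, so several zones may merge. Against that, section 5.1 requires the target zone to lie inside the planned resection, not inside the tumour, so the limits in step 2 are not guaranteed.

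The endpoint is also descriptive, with no hypothesis and no numerical tolerance. That limits the consequence but does not supply a measuring rule.

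**Conclusion.** The concern holds as a weakness in the specified method; it is not evidence that zones will be mismeasured. Followed to the letter, 7.2.6 yields one face that need not pass through the centre of a zone, can miss one, and is blind along the needle.

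The size depends on how much larger the tumour is than the zone. Under the spherical assumptions the loss is about 4% when a 3.1 cm zone sits in a 4 cm tumour. It reaches 13% to 24% only with tumours of at least 3.0 cm (2.0 cm zone) or 5.1 cm (3.1 cm zone), and a complete miss needs a tumour at least twice the zone's diameter. The lack of any view along the needle does not depend on these assumptions.

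The point affects secondary endpoint 1 and part of endpoint 2. It does not touch the primary safety endpoint or the sample size. It is a cheap improvement, best made before the first resection.

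**What to change.** In 7.2.6, with a matching data-capture line in 7.2.2:

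1. For each zone, record the puncture site, needle direction and handle depth reading before withdrawal, and send them with the specimen.
2. Mark the puncture side on the specimen.
3. Cut the whole tumour with surrounding lung into parallel slices at a fixed, stated interval (for example 5 mm) at right angles to the needle axis. Photograph each slice with a scale.
4. For each zone, report the largest cross-section over all slices.
5. Report length along the axis as the number of cut faces showing the zone times the interval, accurate to within about one interval.

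Step 5 should count faces, not partly involved slices. A 2.0 cm length at 0.5 cm spacing crosses on average 2.0/0.5 = 4 faces, giving 2.0 cm, but involves on average 5 slices, giving 2.5 cm (+25%).

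With 5 mm slices, some face lies within 0.25 cm of the zone centre. A spherical 2.0 cm zone then reads at least √(4 − 0.25) = 1.94 cm, and a 3.1 cm zone at least √(9.61 − 0.25) = 3.06 cm.

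**Cost:** modest pathology time on tissue already removed, and one extra data-capture item. Treatment is unchanged.

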## ANET ELECTROSURGERY APPLICATOR PILOT EVALUATION STUDY

STUDY OBJECTIVES	Evaluate the preliminary safety and performance of the ANET Electrosurgery Applicator (ANET) during and after bronchoscopic ablation of a target pulmonary nodule/tumor.
PRIMARY ENDPOINT	Safety provided by the evaluation of peri-procedural, device-related adverse events produced by the ANET device used to ablate a target pulmonary nodule/tumor.
SECONDARY ENDPOINTS	
 
1. Pathological and histological evaluation of the acute thermal effect, produced by the ANET device, on targeted pulmonary nodule/tumor and surrounding tissue to determine if the observed zone of ablation is localized and consistent with the predicted zone of ablation.
 
2. Characterize any effects on surrounding tissue outside the zone of predicted ablation.
 

OBSERVATIONAL ENDPOINT	Characterization of possible immune response changes.
STUDY POPULATION	Adult subjects with confirmed Stage I or Stage II primary lung cancer with a pulmonary nodule/tumor suitable for ablation by the ANET device via EBUS bronchoscopy, prior to planned surgical resection (lobectomy or greater).
STUDY SIZE	Up to 10 subjects will be treated, at up to 5 sites.
STUDY DESIGN	This is a first in human use pilot study. Study subjects who are already scheduled for a surgical resection of their target nodule/tumor will be treated with the ANET RF Applicator. Blood will be drawn pre and post ablation, and at 2-4 weeks post surgery. Following ANET ablation, the subject will undergo lung resection as scheduled. The ablated target nodule/tumor will undergo gross histopathologic assessment. and may undergo immuno-histochemical assessment and microenvironment assessment for immune response.
INCLUSION CRITERIA	
 
1. Subject with Stage I or Stage II primary lung cancer
 
2. Pathological proof of target nodule/tumor type and malignancy with specimen considered adequate for mutational analysis per institutional laboratory standards
 
3. Target nodule/tumor which can be accessed via EBUS bronchoscopy
 
4. Resection/surgical candidate (lobectomy or greater) as standard of care
 
5. Participants must be at least 22 years old and able to provide consent
 

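### The immuno-histochemical criterion for cell death in 7.2.6 is met by viable tissue that is not dividing, and the plan conflicts on whether immuno-histochemistry is done

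*Combined protocol and SAP*

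**What the plan says.** **The criterion.** Section 7.2.6 says: "The immuno-histochemical criterion for cell death in is the lack of expression or proliferation/mitotic index markers in the treated and surrounding tissue". No cut-off, field size or untreated comparison tissue is given.

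**The stains.** The same section makes one stain definite: "Routine staining will be performed with hematoxylin and eosin". Gross and histopathological examination are definite too. The vitality stains are a list "which may include one or more of the following": an anti-mitochondrial antibody, TUNEL, Ki67, PHH3 and Masson's trichrome. Ki67 or PHH3 could therefore be the only vitality marker used. No criterion for cell death on H&E is written down.

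**The use.** Section 7.2.6 says that pathology is to compare the observed with the predicted ablation zone and to describe effects outside it. Those are secondary endpoints 1 and 2 in 4.1.2.

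**Whether immuno-histochemistry is done.** The current text differs by place:

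- 4.1.2, endpoint 1: "Pathological and immuno-histochemical evaluation of the acute thermal effect".
- Synopsis, the same endpoint: "Pathological and histological evaluation of the acute thermal effect".
- 5.1: "The ablated target nodule/tumor will undergo gross, immuno-histochemical and histopathologic assessment".
- 7.2.6: specimens "may be examined by immuno-histochemical methods". The synopsis rows on study design and pathology assessment also make it optional.
- 5.2 and 7.2.5: the tumour will be prepared for such evaluation.
- End of 7.2.6: "The pathologic and immuno-histochemical effect of RFA on nodules/tumors and surrounding tissue will be evaluated by an experienced pathologist".

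**The concern.** A criterion for cell death should separate dead tissue from living tissue. This one, applied to a proliferation or mitotic marker, separates non-dividing tissue from dividing tissue. Living cells that happen not to be dividing fall on the dead side.

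The rule is written for tissue around the treated area as well as within it. A literal reading could therefore enlarge the observed zone (endpoint 1) or report damage outside it that is not there (endpoint 2). These two endpoints are the study's performance result.

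The inconsistent wording adds a compliance question. A site that does no immuno-histochemistry satisfies 7.2.6 but not 5.1, and has delivered endpoint 1 as the synopsis words it but not as 4.1.2 does.

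**Working it through.** The plan gives no figure to reproduce: section 12 states no hypothesis and calls the sample size of 10 arbitrary. The check is of the text.

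**Step 1: read the criterion each plausible way.**

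1. *'or' is a slip for 'of'.* Death is lack of expression of a proliferation or mitotic marker. A viable cell that is not dividing meets this.
2. *'or' is literal and gives alternatives.* Death is lack of expression (of what is not said), or lack of a proliferation or mitotic marker. The second alternative suffices alone, so the result is the same.
3. *Both must be lacking.* This would be stricter, but the sentence does not state a joint requirement. Because 7.2.6 allows a single stain, it would not help where Ki67 or PHH3 is the only one used.

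The inference from 'no marker' to 'not dividing' rather than 'dead' needs only the protocol's own name for these markers.

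**Step 2: ask whether a size can be given.** It would need the proportion p of viable cells that carry the marker, which the documents do not state. As an illustration only, with p assumed and cells treated as independent, the share of viable cells that meet the criterion is 1 − p. The chance that 100 viable cells show no positive cell is (1 − p)^100.

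| Assumed p | 1 − p | (1 − p)^100 |
|---|---|---|
| 0.1% | 99.9% | 90.5% |
| 1% | 99% | 36.6% |
| 5% | 95% | 0.6% |
| 20% | 80% | about 0 |
| 50% | 50% | about 0 |

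The result depends almost wholly on p and on the number of cells examined. Slowly dividing tissue is most exposed; a large field of rapidly dividing tumour is hardly exposed. With neither quantity in the plan, no error in cells or millimetres follows.

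**Step 3: set the wording on immuno-histochemistry side by side.** 4.1.2 puts it in the endpoint and 5.1 makes it definite. The synopsis endpoint does not name it; the synopsis pathology row and the body of 7.2.6 make it optional. The synopsis design row does so too, though that phrase also covers the immune-response assessment. Sections 5.2 and 7.2.5 only require preparation, and the last sentence of 7.2.6 may merely name who reads the slides, so these are weaker evidence. The conflict stands without them.

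**The case against.** The best case on the other side has four parts.

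- *The sentence is corrupt.* A word seems to be missing after 'in', and it might have narrowed the rule to a stain or tissue. This stands as a limit: the intended content cannot be known. What is printed, however, is the only immuno-histochemical criterion in the plan, and replacing 'or' by 'of' does not repair it.
- *The effect is conditional.* Immuno-histochemistry is optional in 7.2.6, gross examination, histopathology and H&E always take place, and nothing says that an immunostain overrides H&E in drawing the zone. This stands, and it is why the point is minor.
- *An experienced pathologist would not apply the rule literally.* Probably so. But the plan allows up to 5 sites, and a written rule that readers must ignore is no basis for consistent readings.
- *The study is a descriptive pilot.* This is true, and no test or error rate is at stake.

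Three stronger readings are tempting but not supported. A reader might infer that the rule runs backwards for TUNEL or suits the anti-mitochondrial antibody. The documents name these stains without saying how each is read, so that is for the study pathologist. A reader might infer that the ablation zones will be wrong. The documents support only that the immuno-histochemical part of the reading could be. Finally, a reader might infer that H&E should simply define the zone, as H&E and trichrome slides were used in the short-term animal study. Those animals were kept for 7 days, which section 3 calls the best time to see cell-killing effects. Here, under 5.2, resection follows at once, so that precedent does not transfer directly.

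**Conclusion.** The criterion is wrong as written, and the point is minor. On either reading of 'or', absence of Ki67 or PHH3 is enough to call tissue dead, and viable non-dividing tissue meets that test. The consequence is confined to the immuno-histochemical reading for secondary endpoints 1 and 2. It arises only if one of these optional markers is used and the rule is applied literally. The number of subjects affected lies between none and the 10 planned, and no size of error per subject can be derived. The primary safety endpoint is unaffected.

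The conflict over whether immuno-histochemistry is part of the assessment is plain from the current text and needs no assumption. The first conclusion assumes that the printed sentence is the operative rule and that the word lost after 'in' does not restrict it.

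**What to change.** 1. **Criterion (7.2.6).** Rewrite the sentence so that absence of Ki67 or PHH3 alone never counts as cell death, and make these two markers descriptive only. Before the first specimen is read, have the study pathologist write down the direction and criterion for each other stain to be used, and for H&E in tissue resected immediately after ablation.
2. **Comparison tissue.** Read any immunostain against unablated tissue on the same resection specimen. Where no unablated tumour remains, use lung only and say so. Do not rely on the pre-treatment specimen, which 8.3.1 describes as collected for mutational analysis.
3. **Reporting.** Report immunostain results by stain, without pooling different stains.
4. **Wording.** State in one consistent way whether immuno-histochemistry is done, in the synopsis, 4.1.2, 5.1, 5.2, 7.2.5 and 7.2.6.

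The cost is a small wording change and slightly more pathology reading. No stain becomes mandatory and subjects undergo no new procedure. The drawback is a weaker control for any subject whose ablation zone covers the whole tumour.
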